The PI or sub-I will be present when the subject takes the study drug or placebo (-120 minutes; see Table 3). At that time, and until the CO₂ inhalation test is about to begin (-120 mins to 0 mins), the Research Coordinator will be present in the room. From the time of the CO₂ inhalation test (0 mins) until the patient leaves accompanied by a friend or family member (+60 mins), both the Research Coordinator and the PI or sub-I will be present in the room.

-130 mins	Patient welcomed to the CRC. Taken to the testing room. Baseline behavioral ratings and vital signs obtained. 7 cc blood drawn (ORX)	PDSS, CGI-S; Vital Signs (VS); ORX
-120mins	Administer single oral dose of suvorexant 10 mg or identical-appearing placebo with water.	
-10 mins	Obtain pre-CO ₂ test baseline behavioral and physiological (vitals) measures.	VAS (5 items), PSS; VS

-5 mins	Plastic mask attached, and patients on room air for 5 minutes. 7cc blood drawn (ORX)	ORX level
0 mins	Blindly switch to 35% CO ₂ / 65% O ₂ gas mixture inhalation for 60 seconds.	
+1 mins	Monitoring for panic/anxiety symptoms, ORX	VAS, PSS, VS, ORX
+5 mins	Monitoring for panic/anxiety symptoms	VAS, PSS, VS
+15 mins	Monitoring for panic/anxiety symptoms, ORX	VAS, PSS, ORX, VS
+30 mins	7 cc blood drawn (ORX)	ORX
+60 mins	Monitoring for panic/anxiety symptoms. If patient stable discharge from the CRC, accompanied by a family member, friend, or caregiver.	VAS, PSS VS

ORX and DNA blood samples: Blood samples for ORX ELISA analysis will be collected, prepared and processed by the study coordinators. The samples will be collected into 7 ml Vacutainer tubes (#VT-6450) which contain EDTA (lavender top). The tubes will be shaken gently several times immediately after collection to promote anti-coagulation. Blood will then be transferred to centrifuge tubes and centrifuged at 1,000 x g for 15 minutes at 4°C. 1 mL plasma samples will be removed, and stored in a -80°C freezer located in the CRC.⁴⁷ From those subjects who have provided their (additional informed consent to allow a blood sample to be collected for future DNA analysis, a sample of this centrifuged blood (after the plasma has been removed) will be banked in a -80°C freezer located in the CRC for future candidate gene/DNA analysis. Genes of interest with respect to ORX metabolism are the preproORX gene and genes that code for the receptors, ORX1 and ORX2.

Suvorexant/Placebo Medication, and Rescue Medication

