Methods for unblinding the study: The treatment code must not be broken except in medical emergencies when the appropriate management of the subject necessitates knowledge of the treatment randomization. In the event of such a patient emergency, the medication blind will be revealed to the appropriate emergency medical staff by the coordinator or PI. Treatment codes will not be broken for the planned analyses of data until all decisions on the evaluability of the data from each individual subject have been made and documented.

Follow-up Contacts

After subjects complete their participation in study visit 2, and as an extra measure to ensure their ongoing well-being, we will

- Make a follow-up phone call to subjects the day after study visit 2, to ask them how they are doing, and to verbally verify that a family member stayed with them the appropriate amount of time after study visit 2.
- Complete one follow-up visit with each subject and the PI or a sub-I at the CRC to ensure that subjects have returned to baseline.

From time of enrollment through return to baseline, subjects will be enrolled in the study approximately two weeks.

Because subjects' participation in the study does not provide any treatment for their condition, after subjects complete their participation in the study, they will be offered the opportunity to receive up to four treatment visits from the PI or a sub-I for their panic disorder, after which they will be referred back to their primary care provider. If subjects choose not to accept the treatment visits, they will be referred back to their primary care provider after the follow-up visit (described above).

Adverse Events/Safety Monitoring

Side effects will be assessed clinically at the patient's study visit by the PI, via serial vital sign monitoring and behavioral monitoring. The PI will present a 6-monthly report of study progress to the UCSF-Fresno/CRMC IRB. This will facilitate recognition of any patterns of adverse events, and provide feedback on managing these better as the study progresses.

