Based on the PI's clinical interaction with and observations of the patient, lorazepam 0.5 mg po will be available for use as a rescue medication if patients have a pronounced or prolonged CO₂ panic response following CO₂ administration. There is evidence in psychiatric patients that acute benzodiazepine ingestion/overdose may not greatly alter CSF ORX levels,⁴⁰ and hence plasma ORX data obtained if patients have had rescue medication may still have validity.

Because of the small risk of somnolence in our study subjects, we will require that subjects not drive home after study visit 2. The day of study visit 2, before any drug is administered, investigators will ensure that the subjects have a plan to be accompanied by a family member, friend or caregiver, and that this individual will be in the subjects' company for the remainder of 7 hours from the time they took the drug. This individual must ensure their transport home and report any adverse events to the investigator at [contact].

In the unlikely event of an adverse reaction requiring medical or psychiatric care, patient coverage will be available 24/7 through the UCSF-Fresno psychiatry on-call schedule, who will be informed that the PI is available to be contacted via cell phone or email at any time. On-call activities and interaction are not charged in Psychiatry. In the unlikely event of additional ED or urgent care treatment, this will be covered by UCSF, depending on a number of factors.

All adverse events that qualify as Unanticipated Problems will be reported to the IRB within 10 days; any subject deaths will be reported to the IRB within 24 hours of a member of the study team learning about the death.

The Safety Monitor

The PI will present this project to [name], MD, the Safety Monitor, for an initial review shortly after IRB approval. Thereafter, 3 monthly monitoring reviews will be conducted with the PI presenting a brief synopsis of adverse events, reasons for drop-out, and study progress. If there is a serious adverse event (e.g. patient hospitalized for medical or psychiatric reasons during the protocol, or a patient death), an emergency meeting with the Safety Monitor will be convened.

Data Management and Statistical Considerations

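### No side-effect enquiry is scheduled at visit 2, and the stated assessor need not be present between capsule and gas, so subjective drug effects may be missed or left without an onset time

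*Combined protocol and SAP*

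**What the plan says.** Adverse Events/Safety Monitoring gives one method: the PI assesses side effects clinically at the visit, "via serial vital sign monitoring and behavioral monitoring". The PI is the only assessor named there.

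The section on the 35% CO₂ inhalation test (Study Visit 2) sets out who must attend. The PI or a sub-I is there when the capsule is taken at -120 minutes. From then until the gas at 0 minutes, "the Research Coordinator will be present in the room", and no physician is required. From 0 to +60 minutes, "both the Research Coordinator and the PI or sub-I will be present in the room".

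The timed visit 2 schedule (Table 3) lists clinical scales, vital signs and orexin samples. Neither it nor Table 2 has an entry for adverse events.

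Three later contacts could bring events to light. A companion, who stays until 7 hours after the dose, is to report any adverse event. Staff telephone patients the next day "to ask them how they are doing". A physician checks at the exit visit, about a week later, that the patient is back to baseline.

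The Safety Monitor's three-monthly reviews are held "with the PI presenting a brief synopsis of adverse events". The analysis text in Data Management and Statistical Considerations does not name adverse events.

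**The concern.** The named assessor and the required attendance do not match for the two hours after dosing. The method also depends on what can be measured or seen. The effects that the protocol itself expects, fatigue and somnolence, are partly subjective: a patient can feel tired with no change in vital signs or visible behaviour.

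The interval before the gas matters because it is the only part of the visit after dosing in which the arms can be compared without the gas, or any rescue lorazepam, added on top. The protocol puts the peak plasma level at 120 minutes, which is when the gas is given, so from that point drug effects and CO₂ symptoms overlap in time. If onset is not recorded, the two periods cannot be separated afterwards.

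At stake are the completeness of the synopsis given to the Safety Monitor and the tolerability information carried into the larger study. The efficacy results are not at stake.

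**Working it through.** The plan's only computed design figure, 25 per group for a later study, has no bearing here. The check has two parts.

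**1. What is recorded, and when (Table 3)**

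| Period | Vital signs | VAS and PSS | Side-effect enquiry |
|---|---|---|---|
| Before capsule | -130 | none listed | none |
| Capsule to gas (-120 to 0) | -10 | -10 | none |
| After gas | +1, +5, +15, +60 | +1, +5, +15, +60 | none |

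- The single set between capsule and gas comes 120 - 10 = 110 minutes after dosing.
- The -130 row mentions baseline behavioural ratings, but the instruments it lists are the PDSS and CGI-S. The first listed VAS and PSS are at -10, so those values show a state after the capsule and cannot show a change since the capsule.
- The VAS covers five mood states, of which fear, nervousness and anxiety are named. The PSS has 27 items that are not listed. Whether either scale captures drowsiness cannot be settled from the documents.
- The first general question about how the patient is comes at the next-day call.

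**2. How likely it is that there is anything to record**

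Inputs: 6 patients on suvorexant (Specific Aim 1), and somnolence of 2% against under 1% on placebo, in non-elderly adults on 10 mg for up to a month (drug safety data, under Suvorexant/Placebo Medication). Applying that 2% to one daytime dose is an assumption. The documents give no single-dose rate for any symptom, so 10% to 30% is assumed as a range.

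Chance of at least one case among 6: 1 - (1 - p)^6.

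- p = 0.02: 1 - 0.98^6 = 0.114, about 11%
- p = 0.10: 1 - 0.90^6 = 0.469, about 47%
- p = 0.30: 1 - 0.70^6 = 0.882, about 88%

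These are chances that a case occurs, and equal the chance of recording one only if every case is found. The documents do not say what share would surface without being asked for. Purely as an illustration, if half did, p is halved:

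- p = 0.01: 1 - 0.99^6 = 0.059, about 6%
- p = 0.05: 1 - 0.95^6 = 0.265, about 26%
- p = 0.15: 1 - 0.85^6 = 0.623, about 62%

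**The case against.** The strongest reply is that the patient is neither unobserved nor unasked. The coordinator is in the room throughout and could notice somnolence. The assessment is described as clinical, which leaves room for ordinary questioning. Patients rate their own mood and panic symptoms at -10, before the gas. The companion, the call and the exit visit follow. All of this stands, but none of it is a structured enquiry with an onset time, and the scales have no listed value from before the capsule.

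Two stronger readings are tempting and should not be drawn.

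- A reader might infer that drug effects go unasked until CO₂ symptoms can hide them. The documents do not support this. Patient-rated scales are completed at -10, and because the PSS items are not given, their overlap with drug effects is unknown. Nor is a side-effect question scheduled later in visit 2; the gap covers the whole visit.
- A reader might infer that a symptom before the gas can only come from the capsule, and that later events cannot be attributed. Neither follows. These are unmedicated panic patients who have fasted, given blood and are awaiting a panic challenge, and the protocol quotes some somnolence on placebo. Causal comparison rests on the randomised, blinded placebo arm. Both arms receive the gas, so events after it can still be compared by arm. Onset time sharpens that comparison but does not create it.

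It is also fair to say that tolerability is not an aim, that the study has 12 patients and one dose of an approved drug, and that a count in groups of 6 will be imprecise.

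Finally, a question at -10 would fall between the baseline ratings and the challenge. It could prime the response, or hint at allocation to the coordinator who stays for the outcome ratings. That objection stands and determines where the question should go.

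**Conclusion.** The point holds as a modest, inexpensive improvement. The sections on safety monitoring and on visit 2 attendance disagree about who is placed to assess side effects between capsule and gas. No side-effect enquiry is scheduled at visit 2, and no summary of events by arm is named. Subjective effects may be missed or recorded without onset; the existing safeguards are real but partial and unstructured.

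The size is uncertain. The chance that at least one of 6 patients has something to record is about 11% if the quoted 2% somnolence rate applies to a single dose, and 47% to 88% if any symptom affects an assumed 10% to 30%. The gap in data collection does not depend on which rate is right.

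**What to change.** 1. Reconcile Adverse Events/Safety Monitoring with the visit 2 procedures on who assesses side effects and when.
2. Add an adverse-event row to Tables 2 and 3, with a note for the next-day call.
3. Ask one fixed open question, worded identically in both arms: has the patient noticed anything unusual since taking the capsule, or since last asked? Ask it after the final VAS and PSS at +60, at the next-day call and at visit 3. Record the term and whether onset was before or after the gas.
4. Add to the analysis text the number of patients with any event by arm, split by onset before and after the gas. The planned counts and percentages for categorical variables already suit this.

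How any event is managed stays as in the protocol.

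The cost is about a minute per contact and one form, with no added visit or staff. The trade-off is recall: at +60 a patient looks back over at most 120 + 60 = 180 minutes to place an onset before the gas. In return, the question comes after every VAS and PSS rating and cannot prime the challenge response.

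### The 7-hour escort runs only from study drug and is not extended when lorazepam rescue is given (minor safety point, cheap to fix)

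*Combined protocol and SAP*

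**What the plan says.** Under Adverse Events/Safety Monitoring the reason given for the escort rule is the small risk of somnolence. The rule has three parts:

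- Driving: "we will require that subjects not drive home after study visit 2".
- Arrangement on the day: "before any drug is administered, investigators will ensure that the subjects have a plan to be accompanied by a family member", or by a friend or caregiver.
- Duration: the companion stays "for the remainder of 7 hours from the time they took the drug". Because the plan is settled before dosing, the drug meant here is the study capsule.

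The same section provides that "lorazepam 0.5 mg po will be available for use as a rescue medication if patients have a pronounced or prolonged" response to CO₂, at the PI's judgement. The only consequence of rescue discussed there is whether the orexin data stay valid.

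The timed schedule for visit 2 (35% CO₂ Inhalation Test Procedures) puts study drug at -120 minutes, CO₂ at 0 and discharge at +60 if the patient is stable and accompanied. The +60 row lists mood and panic ratings and vital signs. It mentions neither lorazepam nor a sedation check.

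The note on urine toxicology and benzodiazepine screening, after the exclusion criteria, gives possible additive sedation from study drug plus a benzodiazepine as a patient-safety reason for screening. Rationale for the Proposed Design puts peak suvorexant concentration at 120 minutes after dosing.

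**The concern.** Rescue can be given only after CO₂, so it falls at or after the stated suvorexant peak. A patient on active drug then receives a second sedative of the kind the protocol itself describes as possibly additive. The sponsor judged that one sedative warrants a companion for 7 hours. Followed to the letter, the rule gives less accompanied time after the second sedative than it requires after the first.

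A clinician can hold back a drowsy patient. That does not lengthen a commitment the companion made before dosing for a fixed period. Staff are blinded and cannot tell which rescued patients have had both drugs, so any adjustment has to apply to all of them.

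What is at stake is patient safety in the hours after discharge. Endpoints, sample size, power and type I error are not affected.

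**Working it through.** The plan offers no calculation on this point, so the check is clock arithmetic on its own schedule. Times are minutes relative to CO₂ = 0.

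**Inputs**
- Study drug at -120 and scheduled discharge at +60 (visit 2 timed schedule).
- Escort of 7 h = 420 min from study drug (Adverse Events/Safety Monitoring).
- Lorazepam at +t. The documents give no time, so t = 1 to 60 is assumed: from the end of the 60-second inhalation to the scheduled departure.
- CO₂ panic rate of about 70% (Rationale for the Use of CO₂ Inhalation) and 6 patients per group (Specific Aim 1).
- Visit 2 length of 3.5 h (Table 2).

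**Escort as written**
- End of escort: -120 + 420 = +300.
- Companion time after a +60 discharge: 300 - 60 = 240 min = 4.0 h.
- Accompanied time left after lorazepam (staff, then companion): 300 - t.
- Earliest scheduled discharge after lorazepam: 60 - t.
- Added escort if 7 h runs from lorazepam: (t + 420) - 300 = 120 + t.

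| Lorazepam at | Accompanied time left | Lorazepam to discharge | Added escort under the fix | Escort end, hours after study drug |
|---|---|---|---|---|
| +1 | 299 min (4.98 h) | 59 min | 121 min (2.02 h) | 9.02 |
| +5 | 295 min (4.92 h) | 55 min | 125 min (2.08 h) | 9.08 |
| +15 | 285 min (4.75 h) | 45 min | 135 min (2.25 h) | 9.25 |
| +30 | 270 min (4.5 h) | 30 min | 150 min (2.5 h) | 9.5 |
| +60 | 240 min (4.0 h) | 0 min | 180 min (3.0 h) | 10.0 |

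A later discharge moves time from companion to staff but leaves 300 - t unchanged.

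**Number affected**
- Expected panics if suvorexant had no effect: 0.70 × 12 = 8.4 overall and 0.70 × 6 = 4.2 on suvorexant.
- Only patients with a strong or lasting response would be rescued, and that share is not given.
- The hard limits are 12 patients rescued and 6 with both drugs.

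**Room in the visit**
- Scheduled length: from -130 to +60 = 190 min. Booked length: 3.5 h = 210 min. Slack: 210 - 190 = 20 min.

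**The case against.** The strongest reply is that no harm is shown. The dose is one 0.5 mg tablet, at least 4 hours of accompanied time remain, and the documents say nothing about how long lorazepam acts. The quoted somnolence rate on suvorexant 10 mg is 2%, against less than 1% on placebo. A reader might infer that the remaining cover is unsafe. The documents do not support that.

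A reader might also take discharge at +60 to be automatic. It is not. The patient must be stable, and the PI or sub-I and the coordinator are in the room until departure. Side effects are followed "via serial vital sign monitoring and behavioral monitoring", and the PI who decides on rescue knows it was given. This answers much of the discharge point, although the schedule names no sedation criterion.

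Further cover exists. Of the companion the protocol says: "This individual must ensure their transport home and report any adverse events to the investigator". It also says that "patient coverage will be available 24/7 through the UCSF-Fresno psychiatry on-call schedule". The next-day call is to "verbally verify that a family member stayed with them the appropriate amount of time after study visit 2", wording that leaves room for a longer stay if the physician asks for one. The only duration stated, however, is the 7 hours from study drug.

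The additive-sedation sentence is about screening for undeclared substances, not supervised rescue, so the protocol does not contradict itself. The pharmacological reasoning still carries over.

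Two other inferences should be resisted. First, consent pages and some protocol text were removed before review, so it cannot be said that no instruction exists anywhere. Second, 8.4 of 12 and 4.2 of 6 are expected values, not upper limits. At a 70% rate the chance of 9 or more panics among 12 is about 49%, and of 5 or more among 6 about 42%.

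Finally, the documents do not derive 7 hours for lorazepam. The figure is carried over from the study-drug rule. That is true, but it is the plan's only standard for accompaniment after a sedative.

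**Conclusion.** The point holds as a minor safety gap. In the text available for review, the escort is fixed at 7 hours from study drug and is not adjusted for a second sedative that the protocol's own reasoning treats as possibly additive. Accompanied time after lorazepam is 5.0 to 4.0 hours, and scheduled discharge can come 59 to 0 minutes after it if the patient is judged stable.

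These ranges assume rescue between +1 and +60 minutes. A later rescue would leave less than 4 hours. How many patients are affected is unknown, with at most 6 exposed to both drugs.

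The case for change rests on consistency with the sponsor's own standard and on low cost. It does not rest on evidence that 4 to 5 hours is too short.

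**What to change.** 1. In Adverse Events/Safety Monitoring, add: 'If lorazepam is given, the 7-hour escort period is counted from the later of study drug and lorazepam, for every rescued patient regardless of arm. Before dosing, the companion is told that this could add about 2 to 3 hours.'
2. In the +60 row of the visit 2 schedule, add: 'If lorazepam was given, its clock time is recorded and the PI or sub-I documents a check for undue sedation before discharge.'

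The rule against driving home stays as it is, and the next-day call would verify the extended period where it applies.

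The cost is a few sentences and one form field. Rescue cannot be predicted, so all 12 planned companions need to be available for up to 3 hours more (10 hours after study drug instead of 7, for rescue by +60). Only companions of rescued patients actually stay. Because the rule ignores arm, some placebo patients will be accompanied longer although they took only one sedative; that is the price of keeping the blind. The sedation check has 20 minutes of slack within the booked visit. Nothing changes in the endpoints, sample size or analysis.

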To address **Specific Aim 1**, we will use a prospective, parallel-group, repeated-measures design to compare behavioral, physiological, and biochemical (plasma ORX) responses in 2 independent, unmedicated groups of PD outpatients (n=6 in each group) at baseline/resting state and after panic provocation due to brief (1 minute) inhalation of a 35% CO₂ / 65% O₂ gas mixture. PD patients will be randomized, in a double-blind manner, to receive either a single, oral dose of the mixed ORX1/2 receptor antagonist, suvorexant (10 mg dose), or identical placebo, 120 minutes before CO₂ challenge.

Exploratory aim: To acquire DNA samples for future candidate gene/DNA analysis. Genes of interest with respect to ORX metabolism are the preproORX gene and genes that code for the receptors ORX1 and ORX2.

Expected results: It is expected that, compared to placebo, suvorexant pretreatment will blunt behavioral, physiological, and biochemical (plasma ORX) responses to 35% CO₂ in PD, due to suppression of CNS ORX hyperactivity. The effect sizes generated from the pilot work will permit planning and powering of a larger-scale study, to definitively address Specific Aim 1.

INNOVATION

The current work promises to determine the human applicability of a novel pathophysiologic concept generated from preclinical science, in this instance the ORX hyperactivity hypothesis of panic/anxiety. Our proposed study will perform rapid clinical testing of the ORX hypothesis with a view to identifying a new class of anxiolytic agents (ORX1 antagonists).¹⁵

This translational, experimental medicine approach is expected to hasten proof-of-concept testing of novel anxiolytics for PD and for all anxiety syndromes where panic attacks are an important clinical feature. Not only does the ORX hyperactivity hypothesis promise to inform new treatment development, but it may also shed light on therapeutic mechanisms of standard antipanic treatments, such as SSRIs.²⁴ In addition, ascertainment of the utility of plasma ORX as a biomarker of illness state and clinical improvement could immediately impact practice.

Furthermore, such a finding may well have future transdiagnostic implications with regard to the pathogenesis of panic symptoms that occur in a variety of psychiatric syndromes (e.g., other anxiety disorders, trauma-related disorders) and in medical disorders with panic as a component, such as chronic obstructive pulmonary disease and chronic asthma.

Public Health Impact of the Project

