Informed consent – DNA sample	X		
Psych Hx/Diagnosis Interview/MINI	X		
Inclusion/exclusion criteria	X		
Medical history	X		
Physical examination	X		
Vital signs	X	X (pre-, during, and post-CO ₂)	
ECG	X		
Comprehensive metabolic panel; CBC w/diff; free T4	X		
Urine pregnancy test (females)	X		
Urinalysis	X		
Urine toxicology screen	X		
Urine benzo screen		X	
SUVOREXANT 10MG/PLACEBO.		X (120 mins pre CO ₂)	
OREXIN LEVELS		X (pre-, during & post- CO ₂ challenge)	
DNA sample (optional: obtained only if additional consent form is signed)		X	
PDSS/CGI clinical scales		X (completed by a study doctor pre-CO ₂)	
Visual Analog Scales (Anxiety) and Panic Symptoms Scale (PSS)		X (completed by subjects pre-, during, and post-CO ₂)	
Interview with MD to verify return to baseline			X

Referral to appropriate doctor to treat panic (if desired)			X
--	--	--	---

35% CO₂ Inhalation Test Procedures (Study Visit 2, see Table 3)

After the screening visit (visit 1), patients will be scheduled in about 1 week for the CO₂ challenge test (study visit 2), which will take place in an exam room in East Medical Plaza (University Neurology Associates).

Upon arrival for study visit 2, each participant will receive a consecutive study code. The master list of study codes will be linked with a random assignment of suvorexant and placebo. The randomization schedule will be generated by [name], using a computer program. The pharmacy will maintain an independent list of the study codes and randomization assignments (to either 10mg suvorexant or placebo).

The following instruments will be used by the PI or sub-I to assess baseline PD clinical severity just prior to the CO₂ test:

- the Clinician's Global Impressions of severity of illness (CGI-S)⁴⁴
- the Panic Disorder Severity Scale (PDSS)⁴⁵

The following instruments will be administered to subjects at baseline and serially throughout the test:

- a change-sensitive, patient-rated, Vertical Analog Scale (VAS) mood ratings (5 mood states including fear, nervousness, anxiety, rated 0-100)⁴⁶
- a Patient Panic Symptom scale (PSS; 27 items, each rated 1-4)⁴⁶

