All data analyses will be performed using SPSS version 22. Continuous variables will be summarized separately in the two PD patient groups using descriptive statistics, including mean, SD, minimum and maximum values. Categorical variables (e.g., presence/absence of a CO₂-panic episode) will be summarized using frequency counts and percentages. Baseline demographic data will be compared between the two groups. Dichotomous and ordinal variables will be examined using Fisher's exact tests, and continuous measures (e.g., peak change from baseline in CO₂-evoked VAS anxiety, and peak change from baseline in plasma ORX) with Wilcoxon rank sum tests. Effect sizes will be generated to facilitate planning of a definitive study.

Since our current pilot data (see p. 3) are so limited, the data generated through this study will enable us to estimate power requirements for a larger study, and to fine-tune the protocol. A speculative power estimate for the larger study, based on our current plasma ORX/CO₂ findings, is as follows:

If we assume a mean \pm SD peak change value of 50 \pm 25 pg/ml for the PD/placebo group, and 30 \pm 25 pg/ml for the PD/suvorexant group, we would have 80% power to detect this difference, with $\alpha=0.05$, utilizing a 2-tailed Students t-test, with 25 patients in each group.

The pilot study timeline will be as follows: 3 months to start up and obtain IRB approval; an 8-month enrollment period, recruiting 1-2 patients per month; and a final month for analysis, poster development, and development of a grant application to fund a definitive study of the research questions being addressed by this pilot work.

References

1. de Lecea L, Sutcliffe JG. The hypocretins/orexins: Novel hypothalamic neuropeptides involved in different physiological systems. *Cell Mol Life Sci.* 1999;56(5-6):473-480.
2. Sakurai T. The neural circuit of orexin (hypocretin): Maintaining sleep and wakefulness. *Nat Rev Neurosci.* 2007;8(3):171-181.
4. Samson WK, et al. Both type 1 and type 2 receptors transmit the behavioral effects of orexin/hypocretin. *The FASEB Journal.* 2007;21(5):A462.

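### The plan tests ordinal variables with Fisher's exact test, which ignores their order, although the Wilcoxon test in the same sentence would keep it (minor; free to improve)

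*Combined protocol and SAP*

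**What the plan says.** The test rule is one sentence in the combined protocol and SAP, Data Management and Statistical Considerations. Its first half, "Dichotomous and ordinal variables will be examined using Fisher", names Fisher's exact test for both variable types. Its second half covers "continuous measures (e.g., peak change from baseline in" VAS anxiety, and ends with "peak change from baseline in plasma ORX) with Wilcoxon rank sum tests". No ordered form of the exact test is named.

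The PSS does not appear in that section. Under 35% CO₂ Inhalation Test Procedures it is described as "a Patient Panic Symptom scale (PSS; 27 items, each rated 1-4". Table 2 lists it in one row with the VAS, "Visual Analog Scales (Anxiety) and Panic Symptoms Scale (PSS", and the visit 2 timetable has both at -10, +1, +5, +15 and +60 minutes; the -10 minute entry reads "VAS (5 items), PSS; VS". The plan does not say whether items or a total are analysed, or whether the PSS counts as ordinal or continuous. CGI-S and PDSS are rated only before CO₂.

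Specific Aim 1 gives the size, "n=6 in each group". The stated product of the pilot is in the analysis section: "Effect sizes will be generated to facilitate planning of a definitive study".

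**The concern.** Aim 1 expects a direction: suvorexant should blunt the response to CO₂. On an ordered scale with more than two levels, Fisher's test asks only whether the two distributions differ in any way. It can miss a consistent shift, and it can give a small p where there is no shift at all. The Wilcoxon test, already in the plan, uses the order and handles ties through midranks.

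What is at stake is the sensitivity of the comparison for anything analysed as ordinal. The PSS is the only Aim 1 response measure that could be affected, because it is one of the two patient-rated responses and the plan places it under neither rule.

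**Working it through.** **The plan's own figure.** The one computed figure in the section is 25 per group for the future study (50 v 30 pg/ml, SD 25, 80% power, two-sided 0.05). It reproduces: 2 × (1.960 + 0.842)² × (25/20)² = 24.5, rounded up to 25. The point below does not depend on it.

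**Inputs.** From the plan: 6 v 6 patients, and item levels 1-4. Assumed: the illustrative counts, the level probabilities, and a two-sided 0.05 threshold for the pilot (the plan states 0.05 only for the future study). Fisher's test on more than two levels is taken as the usual unordered 2 × k exact test.

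**One four-level item.** Counts at levels 1-4: placebo 0,1,2,3; suvorexant 3,2,1,0. Each level then holds 3 patients, and there are C(12,6) = 924 allocations.

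*Fisher.* The number of allocations giving placebo counts a,b,c,d is C(3,a)·C(3,b)·C(3,c)·C(3,d).

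| Placebo counts, in any order | Tables | Allocations each | Total |
|---|---|---|---|
| 0,0,3,3 | 6 | 1 | 6 |
| 0,1,2,3 | 24 | 9 | 216 |
| 0,2,2,2 | 4 | 27 | 108 |
| 1,1,1,3 | 4 | 27 | 108 |
| 1,1,2,2 | 6 | 81 | 486 |

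The total is 924. The observed table has weight 9, so p = (6 + 216)/924 = 0.240. All 24 orderings of 0,1,2,3 count as equally extreme, which is how the direction is lost.

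*Exact Wilcoxon.* The midranks are 2, 5, 8 and 11. The placebo rank sum is 1×5 + 2×8 + 3×11 = 54, against an expected 39. Only 0,1,2,3 (9 allocations) and 0,0,3,3 (1 allocation) reach 54 or more. Two-sided p = 2 × 10/924 = 0.022.

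*Mann-Whitney probability.* The placebo patient at level 2 contributes 4, the two at level 3 contribute 2 × 5.5 = 11, and the three at level 4 contribute 3 × 6 = 18. That is 33/36 = 0.92, counting ties as one half.

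*Reverse case.* Counts 3,0,0,3 v 0,3,3,0 have no directional shift. Fisher gives p = 6/924 = 0.006; Wilcoxon gives p = 1.00.

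**Power and type I error.** Full enumeration of all pairs of 6-patient tables:

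| Assumed probabilities, levels 1-4 (other group reversed) | Fisher | Exact Wilcoxon |
|---|---|---|
| .1, .2, .3, .4 | 15% | 25% |
| .05, .15, .30, .50 | 40% | 59% |
| .25 each, both groups (null) | 2.9% | 2.9% |

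In this null setting the two tests have the same error, so the extra power does not come from a looser test.

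**A PSS total, only if it were put under Fisher.** Over all tie patterns of 12 patients, the smallest attainable p depends on the number of distinct values. It occurs when all ties sit in one block:

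- 8 values (5 tied): [C(7,6) + C(7,1)]/924 = 14/924 = 0.015
- 9 values (4 tied): [C(8,6) + C(8,2)]/924 = 56/924 = 0.061
- 10 values (3 tied): [C(9,6) + C(9,3)]/924 = 168/924 = 0.18
- 11 values (2 tied): [C(10,6) + C(10,4)]/924 = 420/924 = 0.45
- 12 values: 924/924 = 1.0

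With 9 or more distinct values, Fisher therefore cannot reach 0.05, even if the groups separate completely. With 12 distinct values and complete separation, exact Wilcoxon gives p = 2/924 = 0.0022.

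**The case against.** The strongest reply is that no named outcome suffers. The section names three outcomes: CO₂-panic yes/no, for which Fisher is suitable, and peak changes in VAS anxiety and plasma ORX, which go to Wilcoxon. The continuous examples are introduced as examples, not as a full list. The PSS is scheduled beside the VAS throughout, so the natural reading is that a PSS total would be handled in the same way. This stands: on that reading the loss is zero. What remains is a stated rule that is inferior wherever it is applied, and a text that does not say where the PSS falls.

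The illustrations can also be challenged. The plan describes neither an item-by-item PSS analysis nor a cross-tabulated total, and mirror-image monotone shifts suit a rank test. That is fair; the figures show the mechanism under labelled assumptions.

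Three stronger readings are tempting, and the documents support none of them:

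- *That the PSS comparison in Aim 1 cannot succeed.* The limit at 9 or more distinct values is conditional on classing the total as ordinal, which the plan nowhere does.
- *That the pilot will yield no effect size reflecting order.* The plan promises effect sizes in a separate sentence and does not tie them to the test.
- *That Fisher's test is wrong here.* It is valid, including for panic yes/no.

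**Conclusion.** The point holds as a minor matter of efficiency. The plan's rule for ordinal variables discards order that another test in the same sentence would use. For a four-level item with 6 per group, the cost in the two assumed shifts is about 10 and 19 percentage points of power (15% v 25%; 40% v 59%).

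The reach is narrow: single PSS items, a PSS total only if classed as ordinal, and CGI-S or PDSS only as baseline comparisons. None of these figures is the trial's expected loss. The weight is low because this is a 12-patient pilot with no stated decision rule, whose product is effect sizes. The undefined PSS summary alone would be only a missing detail, but the same edit can settle it.

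**What to change.** Before unblinding, move ordinal measures to the Wilcoxon half of the sentence and name the PSS there, for example:

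> Fisher's exact test will be used for dichotomous variables, such as CO₂-panic yes/no. Ordinal and continuous measures, including the peak changes from baseline in VAS anxiety, PSS total score and plasma ORX, will be compared by exact two-sided Wilcoxon rank sum tests, with midranks for ties.

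This assumes that the total is the intended PSS summary, which the sponsor should confirm. Optionally, report the Mann-Whitney probability with a 95% confidence interval as the effect size for the ranked measures, since it carries the order forward to the larger study.

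The cost is a wording change, with no extra patients or measurements. The statistician should check that the planned SPSS version 22 installation gives the exact p-values with ties and, if wanted, the interval; if not, the software line needs one addition.
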